3.4.4. Key Secondary Efficacy Analyses**3.4.4.1. Estimands**

Clinical remission by adapted Mayo Score will be analyzed through a composite strategy as follows:

- Population: Same as primary estimand
- Variable: Endpoints (Section 3.4.1) and Definition (3.4.3). Subjects meeting criteria for ICE, with the exception of ICE criteria 6, will have their remission status at Week 8 set to not in remission.
- Intercurrent Events: Intercurrent events outlined in Section 3.3.4.1.
- Population-level summary: The difference in proportion in clinical remission by adapted Mayo Score between each TD-1473 group and placebo.

3.4.4.2. Analysis Methods

Subjects meeting criteria for ICE, with the exception of ICE criteria 6, will follow a composite strategy with their remission status at Week 8 set to not in remission. Subjects meeting ICE criteria 6 will have their Week 8 remission status missing and not imputed and assumed MCAR. The proportions of subjects with clinical remission by aMS definitions will be compared between each TD-1473 treatment group and the placebo group using a Cochran-Mantel-Haenszel (CMH) chi-square test stratified by biologic failure status (yes or no) and corticosteroid use at baseline (yes or no). In order to derive the weighed difference in proportions, CMH weights (w_j) will be used:

$$\hat{w}_j = \frac{\left(\frac{n_{1j}n_{2j}}{n_{1j}+n_{2j}} \right)}{\sum_{j=1}^4 \left(\frac{n_{1j}n_{2j}}{n_{1j}+n_{2j}} \right)} \text{ For } j=1 \dots 4 \text{ stratum}$$

To derive the difference in proportions within a stratum, the standard difference in proportions is used, $\hat{d}_j = \hat{p}_{2j} - \hat{p}_{1j}$ where the difference over all strata is $\hat{d}_{CMH} = \sum_{j=1}^4 \hat{w}_j \hat{d}_j$.

A Wald-type CI is constructed as follows:

$$\hat{d}_{CMH} \pm (z_{\alpha/2} \times \hat{\sigma}(\hat{d}_{cmh}))$$

Where $\hat{\sigma}(\hat{d}_{cmh})$ is estimated with the Sato variance estimator (Sato, 1989).

Summaries of the proportion of subjects in remission will be presented by treatment group, the adjusted treatment difference in proportions between each TD-1473 group and placebo will also be presented along with associated 95% CIs calculated based on the Wald method outlined above. P-values from the CMH Chi-square test for the comparison of each dose of TD-1473 versus placebo will also be presented.

Separate 3-group forest plots for the difference in proportion versus placebo at Week 8 will display the CMH weighted difference in proportions and associated 95% CI.

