3.3.6.3. Subgroup Analysis

To characterize the consistency of the treatment effect for the primary and supplementary estimands, the primary endpoint analysis will be repeated for each examination group specified below.

The subgroups will be analyzed with the inclusion of an interaction term of treatment*subgroup category and baseline*subgroup category into the primary analysis model. If a subgroup determines the level of a class effect included in the primary analysis model, the redundant term will be omitted (e.g., prior biologic failure status subgroup analyses will not include the status term). Treatment group LS means for each subgroup will be calculated by setting the baseline score to the subgroup mean (for the subjects included in the analysis).

The following subgroups are pre-defined:

- Biologic Failure Status: [a] Yes, [b] No

- Biologics experience categories: [a] Primary non-responder, Secondary non-responder or intolerant, [b] naïve, [c] bio-experienced [but not documented failure]
- Number of prior biologics failed [a] 0 [b] 1 [c] ≥ 2
- Number of biologic classes failed [a] 0 [b] 1 [c] ≥ 2
- Inadequate response to at least one biologic: [a] Yes, [b] No
- Intolerant to at least one biologic: [a] Yes, [b] No
- Steroid use status at enrollment: [a] Yes, [b] No
- Baseline Tobacco use Status: [a] no use [b] prior use [c] current use
- Extent of disease: [a] Proctosigmoiditis, [b] Left-sided colitis, [c] extensive
- Duration of disease: [a] ≤ 5 years, > 5 to ≤ 15 years, > 15 years

■ [REDACTED]

■ [REDACTED]

- Baseline total Mayo score: [a] ≤ 10 [b] > 10
- Baseline adapted Mayo score: [a] ≤ 7 [b] > 7
- Baseline Mayo Endoscopy subscore [a] 2 [b] 3
- Baseline Rectal Bleeding subscore [a] 0 [b] ≥ 1
- Geographic Region: [a] North America [b] Eastern Europe [c] Europe (excluding Eastern Europe) [d] Asia/Pacific [e] Other;
- Country: [a] Japan [b] United States [c] Rest of the world
- Refractory or intolerant to 6-MP/AZA: (yes, no)
- Refractory, dependent or intolerant to oral or IV corticosteroids: (yes, no)
- Evidence of inadequate response, recurrent disease or relapse to 6-MP/AZA OR corticosteroids: [a] yes to both, [b] No to 6-MP/AZA and yes to steroids, [c] yes to 6-MP/AZA and no to steroids, [d] No to both

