3.4.6.2. Subgroup Analyses

All subgroup analyses outlined for the primary endpoint will be performed on clinical remission by aMS at Week 8 and change from baseline in aMS at Week 8.

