3.6.4. Supplementary Analyses

3.6.4.1. Subgroup analysis

To characterize the consistency of the treatment effect for clinical response by aMS and tMS, endoscopic healing, and endoscopic remission, subgroup analyses will be performed for each of the subgroups in Section 3.3.6.3.

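### Phase 2b SAP: the Wald/Sato interval for the remission difference is too short in the smallest subgroups, and no sparse-data rule is given

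*SAP*

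**What the plan says.** Section 3.4.4.2 of the Phase 2b SAP compares remission at Week 8 between each dose and placebo by a CMH test over four strata (prior biologic failure by corticosteroid use). It forms a CMH-weighted difference in proportions. For the interval, "A Wald-type CI is constructed as follows": the estimate plus or minus a normal quantile times a standard error from the Sato variance. Results are reported with "associated 95% CIs calculated based on the Wald method outlined above".

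Section 3.4.6.2 adds that "All subgroup analyses outlined for the primary endpoint will be performed on clinical remission by aMS at Week 8". The list in section 3.3.6.3 shows 19 factors with 50 levels, besides two redacted bullets. With three doses that is about 50 × 3 = 150 dose-placebo intervals. One factor is "Geographic Region: [a] North America [b] Eastern Europe [c] Europe (excluding Eastern Europe) [d] Asia/Pacific [e] Other"; another crosses 6-MP/AZA history with steroid history in four levels. Section 3.3.6.3 says that "the primary endpoint analysis will be repeated for each examination group specified below", but the model it then describes is an ANCOVA with interaction terms, which does not fit a binary outcome.

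**The concern.** A Wald interval takes its width from the observed event counts. With few subjects and low remission rates those counts are often zero or one, and the estimated variance is then too small. In the extreme, a subgroup with no remitter on either arm gets an interval of zero width.

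These subgroup analyses are there to show whether the effect is consistent, and remission is the primary endpoint planned for Phase 3 Induction. If the intervals shrink where data are thinnest, the least informative subgroup looks the most precise on a forest plot, and a real effect can appear to be excluded.

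**Working it through.** **The plan's own figure first.** Section 1.5 of the SAP gives about 90% power for all three doses (protocol 8.2.1: 89%) and more than 98% for at least one, with 60 per arm, a 2-point effect, SD 3 and Hochberg. Simulation gives 89.0% and 98.4%. With SD 3.5 it gives 73.9% and 93.8%, against 73% and 94% stated. So 60 per arm is a reproducible starting point. The documents state no interval coverage beyond the nominal 95%.

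**Inputs.**
- 60 per arm, 1:1:1:1 (SAP 1.5 and 1.2.1).
- Four strata (SAP 3.4.4.2), taken as equal in size; this is an assumption.
- Remission 9.5% on placebo, 23.5% and 16.5% on active (protocol 8.2.2). These are Phase 3 planning values; using them for Phase 2b is an assumption.
- A lower pair, 5% v 10%, as an assumed alternative. Section 3.4.4.3 counts missing data as non-remission, which pushes rates down.

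**How small the levels must be.** One dose plus placebo is 120 subjects.
- Five regions: 120 / 5 = 24, so some region has 24 or fewer over both arms, an average of 12 or fewer per arm.
- Four 6-MP/AZA-by-steroid levels: 120 / 4 = 30, so some level averages 15 or fewer per arm.
- Biologic failure: the protocol's soft caps (3.5.2) aim for 40% to 60%, so 0.4 × 60 = 24 to 0.6 × 60 = 36 per arm.

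At 12 per arm and planning rates, the expected remitters are 12 × 0.095 = 1.1 on placebo and 12 × 0.235 = 2.8 on active.

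**Zero width.** The Sato variance is (d ΣP + ΣQ) / (Σ n1n2/N)². Every term of Q carries a remitter count as a factor. With no remitter on either arm, d = 0 and ΣQ = 0, so the variance is exactly 0 and the interval is [0, 0]. The CMH statistic is then 0/0. Ignoring strata, the probability of this is [(1 − p_placebo)(1 − p_active)]^n. At 10 per arm:
- 9.5% v 23.5%: (0.905 × 0.765)^10 = 0.692^10 = 2.5%. With four strata, simulation gives 3.4%, because strata lacking one arm drop out.
- 9.5% v 9.5%: (0.905 × 0.905)^10 = 13.6%. With four strata, 15.6%.

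**Coverage of the nominal 95% interval, four strata, simulated.**

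| Per arm | 9.5% v 23.5% | 5% v 10% (assumed) |
|---|---|---|
| 60 | 94.5% | 94.4% |
| 36 | 94.1% | 94.1% |
| 24 | 93.4% | 90.0% |
| 15 | 92.1% | 86.1% |
| 12 | about 90% | about 80% |
| 10 | 86.7% | 73.9% |

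At 9.5% v 16.5% (the protocol's less effective dose), coverage is 89.8% at 15, about 89% at 12 and 85.7% at 10. If both rates are 9.5%, coverage is 94% to 96% at every size, because an interval of [0, 0] contains the true value of zero. Removing the strata helps only a little: at 10 per arm, coverage is 89.1% at planning rates and 75.5% at 5% v 10%.

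**Comparator.** A stratified Miettinen-Nurminen interval with the same CMH weights, at 9.5% v 23.5%, covers 95.0% at 60 per arm, 95.6% at 24, 96.5% at 15 and 97.8% at 10. It does not collapse when there are no remitters.

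**The case against.** The strongest reply is that nothing confirmatory depends on these intervals. The key secondary p-value comes from the CMH test, the interval is sound at 60 per arm, and the subgroup results are supplementary. The visible dose-selection framework in protocol 8.11 does not mention subgroups. All of this stands.

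Second, the SAP never says that the four-stratum Wald/Sato calculation is rerun inside each level. That also stands as a matter of wording. But it is the only method shown for the remission difference, and the ANCOVA in 3.3.6.3 cannot be applied to a binary endpoint, so it is the natural reading.

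Third, subgroup sizes are mostly unknown. Of the 19 visible factors, 10 have two levels and 7 have three. Averages force 15 or fewer per arm only for region and the 6-MP/AZA-by-steroid split. Small numbers in Japan, for example, are plausible but assumed.

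A reader might infer that many subgroups have about 5 per arm, where simulated coverage at planning rates falls to 63% with 28% zero-width intervals. No document establishes that size. A reader might also extend the point to response and endoscopic endpoints, since section 3.6.4.1 says "subgroup analyses will be performed for each of the subgroups in Section 3.3.6.3". Their analysis methods are redacted, so that extension is unsupported.

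Finally, if 0/n v 0/n is printed beside a [0, 0] interval, a careful reader is partly protected; a forest plot alone offers no such warning.

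**Conclusion.** The point holds for the remission intervals in small subgroups and nowhere else. The main comparison is sound. The biologic-failure subgroups, at 24 to 36 per arm, are close to nominal at planning rates (93.4% to 94.1%), though coverage would be about 90% at 24 per arm under 5% v 10%. At the sizes that averages force for two factors, the shortfall at planning rates is about 3 points at 15 per arm and 5 at 12. It grows to about 8 points at 10 per arm and is larger at lower remission rates.

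The undercoverage needs a true difference; at equal rates of 9.5% the method does not manufacture subgroup effects. Zero-width intervals occur either way. The size rests on Phase 3 planning rates, equal strata, and the reading that section 3.4.4.2 is what runs within each level. The documents do not support inferring that the key secondary result is unreliable.

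**What to change.** In section 3.4.6.2, state that the remission difference within each subgroup level is reported with a stratified Miettinen-Nurminen score interval using the CMH weights of section 3.4.4.2. Also report, for each level, the number of subjects in strata that lack one of the two arms, since those strata carry zero weight and their subjects otherwise drop out unseen. The same interval could replace the Wald form in 3.4.4.2 for consistency, but the main analysis does not need it.

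The point estimate, the CMH test and the multiplicity plan stay as they are. There should be no automatic switch to an unstratified interval when a stratum lacks an arm, because estimates would then not be comparable across subgroups.

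The cost is a sentence or two in the SAP and a change of interval method in the programming. Intervals in small subgroups become wider, asymmetric and somewhat conservative (97.8% coverage at 10 per arm at planning rates).

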3.4.4.3. Missing Data Handling

Following the application of ICE strategy, missing data will be imputed as not in remission .

3.4.5. Sensitivity Analyses

No sensitivity analysis will be performed for secondary endpoints.

3.4.6. Supplementary Analyses

3.4.6.1. Change in aMS

Change in aMS at Week 8 will be analyzed by fitting an ANCOVA model incorporating the change from baseline aMS measurement at Week 8 as the dependent variable in the model. The model will include independent fixed-effect class terms for treatment group, prior biologic failure status (yes/no), corticosteroid use at baseline (yes/no). A covariate for baseline aMS will also be included.

The analysis population, intercurrent events and missing data will be analyzed in the same way as for the primary estimand. Summaries will include observed values, change from baseline values and least square (LS) means estimates. Each TD-1473 dose versus placebo will be compared by displaying the LS mean difference estimate to placebo and associated 95% confidence interval. Nominal p-values will also be reported.

A 4-group forest plot will summarize the LS mean change from baseline in aMS at Week 8 with 95% confidence interval. An additional 3-group forest plot will summarize the difference from placebo in LS mean change from baseline in aMS at Week 8 with 95% confidence interval.

3.4.6.2. Subgroup Analyses

All subgroup analyses outlined for the primary endpoint will be performed on clinical remission by aMS at Week 8 and change from baseline in aMS at Week 8.

3.4.6.3. Adapted Mayo Score Completeness

Summaries of the completeness of Adapted Mayo Score components at Week 8 will be performed where the number of patients missing 1, 2 or all components will be presented. For subjects with all components missing the summary will be further broken down by those of discontinue prior to Week 8 and those who missed the Week 8 visit.

The number of subjects who experience an intercurrent event prior to Week 8 and those who don't will also be presented for the subset of subjects with at least one Adapted Mayo Score component missing at Week 8.

- [REDACTED]
- [REDACTED]
- [REDACTED]
- [REDACTED]
- [REDACTED]
- [REDACTED]
- [REDACTED]
- [REDACTED]
- [REDACTED]
- [REDACTED]
- [REDACTED]
- [REDACTED]
- [REDACTED]
- [REDACTED]
- [REDACTED]
- [REDACTED]

3.6.2. Definition of Exploratory Endpoint(s)

[REDACTED]

[REDACTED]

[REDACTED]

[REDACTED]

[REDACTED]

[REDACTED]

[REDACTED]

[REDACTED]

[REDACTED]

[REDACTED]

[REDACTED]

[REDACTED]	[REDACTED]	[REDACTED]
[REDACTED]	[REDACTED]	[REDACTED]
[REDACTED]	[REDACTED]	[REDACTED]
[REDACTED]	[REDACTED]	[REDACTED]
[REDACTED]	[REDACTED]	[REDACTED]

[REDACTED]

[REDACTED]

[Redacted]

[Redacted]	[Redacted]	[Redacted]	[Redacted]	[Redacted]	[Redacted]	[Redacted]
[Redacted]	[Redacted]	[Redacted]	[Redacted]	[Redacted]	[Redacted]	[Redacted]

[Redacted]

[Redacted]

[Redacted]

[Redacted]

[Redacted]

[Redacted]

[Redacted]

[Redacted]

[Redacted]

[Redacted]

[Redacted]

[Redacted]

[Redacted]

[Redacted]

[Redacted]

[Redacted]

[Redacted]

[Redacted]

[Redacted]

[Redacted]

[Redacted]

[Redacted]

[Redacted]

[Redacted]

[Redacted]

[Redacted]

[Redacted]

[Redacted]

[Redacted]

[Redacted]

[Redacted]

[REDACTED]

[REDACTED]

[REDACTED]

[REDACTED]

[REDACTED]

[REDACTED]

[REDACTED]

[REDACTED]

[REDACTED]

[REDACTED]

- [REDACTED]

- [REDACTED]

[REDACTED]

[REDACTED]

[REDACTED]

[REDACTED]

[REDACTED]

[REDACTED]

[REDACTED]

[REDACTED]

- [REDACTED]

- [REDACTED]

[REDACTED]

[REDACTED]

[REDACTED]

[REDACTED]

[REDACTED]

[REDACTED]

[REDACTED]

[REDACTED]

[REDACTED]

[REDACTED]

[REDACTED]

[REDACTED]

[REDACTED]

[REDACTED]

[REDACTED]

[REDACTED]

[REDACTED]
[REDACTED]
[REDACTED]
[REDACTED]

3.6.4. Supplementary Analyses

3.6.4.1. Subgroup analysis

To characterize the consistency of the treatment effect for clinical response by aMS and tMS, endoscopic healing, and endoscopic remission, subgroup analyses will be performed for each of the subgroups in Section 3.3.6.3.

3.7.1. Extent of Exposure

Study drug exposure will be summarized using the 8-point descriptive summary presenting number of doses and duration of treatment separately for the induction phase and complete study separately.

Duration of treatment will be displayed in weeks and calculated for the induction period as:

$$\frac{(last\ induction\ phase\ dose\ date - first\ dose\ date + 1)}{7}$$

*Last induction phase dose date is the Week 8 visit dose administration date for those that reach the Week 8 visit or equal to date of last study drug return for those who discontinue prior to Week 8 visit.

Duration of treatment for the entire study period will also be displayed in weeks and calculated as:

$$\frac{(last\ study\ drug\ return\ date - first\ dose\ date + 1)}{7}$$

Calculated values will be rounded to 1 significant digit in the analysis datasets and summary statistics will be presented to the follow significant digits:

- Mean, median, Q1, Q3: 1 significant digit
- Standard deviation: 2 significant digits
- Minimum, maximum: 1 significant digit

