8.8.1. Extent of Exposure

Extent of exposure will be calculated from data collected in the study drug administration page of the CRF and summarized. Reasons for study drug discontinuation will be summarized. For each subject, treatment compliance over the interval from first to last dose will be calculated from data collected in the study drug administration and drug accountability pages of the eCRF. Treatment compliance will be summarized by actual treatment received.

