- Subject should be instructed not to take study drug from their Induction study drug bottles at home to allow for re-randomization and to receive the first dose of extended induction in the clinic.

4. Week 16 visit may be done over a period of 1 to 3 visits to complete: a) the Week 16 endoscopy, b) Week 16 clinical assessments (e.g., vital signs, weight, laboratory testing, and Quality-of-Life assessments), and c) an optional visit to bring subjects back (or could be done over the phone) to inform them that they should stop study drug and proceed to EOS visit if they did not achieve clinical response (those who achieve clinical response will proceed to mWeek 0 visit). The Week 16 clinical response will be determined using the adapted Mayo score utilizing the centrally read endoscopic subscore from the Week 16 endoscopy.
5. Early Study Drug Discontinuation visit is for subjects who prematurely discontinue the Study drug during the Induction Study. Visit to be conducted within 5 days of the last dose of Study drug, if possible. Subject will also return for the EOS visit for collection of safety data and assessment of disease activity four weeks after last study drug. An EOS visit will be required for all subjects 4 weeks following their last dose of study drug, regardless if they completed the full duration of study drug treatment.
6. Seven-day window provided to allow time to receive results from the central reading of endoscopy performed at Week 8a.
7. Blood pressure and heart rate will be measured after the subject has been resting for at least 5 minutes in the seated or supine position. Vital sign measurements should be obtained prior to scheduled blood draws.
8. Obtain blood pressure and heart rate pre-dose and approximately 1-hour post-dose on Day 1.
9. ECGs should be performed after the subject has been resting in a supine position for at least 10 minutes.
10. Physical Exam will be performed as per local standard practice.

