3.7.1. Extent of Exposure

Study drug exposure will be summarized using the 8-point descriptive summary presenting number of doses and duration of treatment separately for the induction phase and complete study separately.

Duration of treatment for the study will be displayed in weeks and calculated as:

$$\frac{(\text{last study drug return date} - \text{first dose date} + 1)}{7}$$

Calculated values will be rounded to 1 significant digit in the analysis datasets and summary statistics will be presented to the follow significant digits:

- Mean, median, Q1, Q3: 1 significant digit
- Standard deviation: 2 significant digits
- Minimum, maximum: 1 significant digit

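### Both SAPs end treatment duration at the study drug return date instead of the last dose, overstating exposure by up to 5 days or by about 4 weeks, depending on the visit at which drug comes back

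*SAP*

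**What the plan says.** Section 3.7.1 of the Phase 2b SAP defines two durations in weeks, each as (end date − first dose date + 1)/7.

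- **Induction period.** The end date is called the last induction phase dose date. "Last induction phase dose date is the Week 8 visit dose administration date for those that reach the Week 8 visit"; it is "or equal to date of last study drug return for those who discontinue prior to Week 8 visit".
- **Entire study.** "Duration of treatment for the entire study period will also be displayed in weeks and calculated as" a formula whose end date is the "last study drug return date". This applies to every subject. Section 3.7.1 of the Maintenance SAP repeats the formula.

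The same section adds: "Calculated values will be rounded to 1 significant digit in the analysis datasets".

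The protocol names a different source. Section 8.8.1 reads: "Extent of exposure will be calculated from data collected in the study drug administration page of the CRF".

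The Phase 2b SAP uses the last dose date elsewhere: in the disposition listing (3.2.1), the compliance denominator (3.7.1.1) and the end of the treatment-emergent window (3.7.2). Appendix 1 of each SAP, which records changes to protocol-planned analyses, does not mention a move to the return date.

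**The concern.** A return date records when bottles came back to the site. It can fall on or after the last dose, so using it as the end of treatment credits subjects with days on which they took nothing. In Induction this touches only subjects who stop before Week 8. In the whole-study figure it can touch anyone.

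At stake is the exposure table by dose, which is the background for reading adverse events and tolerability in a dose-finding study. Protocol 8.11 gives the Dose Selection Committee unblinded safety summaries. Within the Phase 2b SAP, one subject could also show two different treatment end dates in adjacent safety outputs: one in the exposure table, another in the compliance and adverse event tables.

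**Working it through.** The documents give no figure to reproduce here, so the check is date arithmetic.

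**Excess per subject.** Let F be the first dose date, L the last dose date and R the return date.

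(R − F + 1)/7 − (L − F + 1)/7 = (R − L)/7 weeks

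**Possible lags, R − L.**

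- *Discontinuation visit.* Footnote 5 to the Schedule (Phase 2b SAP 1.4) says: "Visit to be conducted within 5 days of the last dose of Study drug, if possible". The lag is 0 to 5 days. Protocol 6.3.13 does not request this visit after withdrawal of consent.
- *EOS visit.* This is 4 weeks after the last dose, with a window of −3 to +5 days: 28 − 3 = 25 to 28 + 5 = 33 days.
- *Week 16 non-responders.* Protocol 5.2.1.1 has them continue dosing until non-response is established. Footnote 4 describes the last contact as an optional visit, "or could be done over the phone) to inform them that they should stop study drug and proceed to EOS visit". The discontinuation visit is meant for premature stoppers, so after a phone call the next scheduled visit is EOS.

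Protocol 5.5 says only that drug is returned at each applicable visit, and no drug-return row is visible in the Schedule. Which lag applies is therefore an inference.

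**Duration in weeks under the SAP formula.**

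| Lag (days) | Excess (weeks) | Last dose Day 14 (true 2.0) | Last dose Day 28 (true 4.0) | Week 16 non-responder, last dose Day 112 (true 16.0) |
|---|---|---|---|---|
| 5 | 5/7 = 0.71 | 19/7 = 2.7 | 33/7 = 4.7 | not the planned path |
| 25 | 25/7 = 3.57 | 39/7 = 5.6 | 53/7 = 7.6 | 137/7 = 19.6 |
| 28 | 28/7 = 4.00 | 42/7 = 6.0 | 56/7 = 8.0 | 140/7 = 20.0 |
| 33 | 33/7 = 4.71 | 47/7 = 6.7 | 61/7 = 8.7 | 145/7 = 20.7 |

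**Mean Induction excess per arm** = proportion stopping early × lag/7. The documents give no early-stop rate. The nearest reference is the 10% replacement trigger in protocol 6.6.2. Assuming 5%, 10%, 15% and 20%:

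- all return at 5 days: 0.04, 0.07, 0.11 and 0.14 week;
- all return at 28 days: 0.2, 0.4, 0.6 and 0.8 week.

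**Subjects who reach Week 8.** In-clinic dosing is scheduled at Week 8b (footnote 28) and at mWeek 0 (protocol Table 2), not at Week 8a. On that reading, the dose that ends Induction duration is the first dose of the next period; for placebo non-responders it is TD-1473 80 mg. Section 3.1.5.1 closes the Induction period at that same dose. The difference is about one day.

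**Rounding.** Taken literally, 1 significant digit turns 16.4 weeks into 20 and 44 weeks into 40.

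**The case against.** The strongest reply is that the planned path for an early stopper is a discontinuation visit within 5 days, so the excess is normally at most 0.7 week. That stands. A reader might infer that early stoppers generally gain 4 weeks, or that the error falls mainly on them. The documents support neither. For an early stopper, the long lag requires the discontinuation visit to be missed or not requested and drug to be handed back at EOS. The whole-study formula covers everyone, and the phone route for Week 16 non-responders concerns subjects who completed treatment. Nor is 4 weeks a ceiling, since the EOS window alone allows 33 days.

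A reader might also infer that compliance is corrupted: drug stopped on Day 14 and returned on Day 42 would score 14/42 = 33% and become a major analysis deviation. Section 3.7.1.1 rules this out as written, because its denominator ends at the date of last dose. The per-protocol set requires a completed Week 8 visit in any case, so these subjects are already outside it.

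A third tempting reading is that poor tolerability of one dose would be hidden. That stopping is dose-related is a hypothesis, not something the documents state. Adverse events are reported as counts and percentages of subjects, the visible text has no exposure-adjusted rates, and number of doses, dose dates and discontinuations are also reported.

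Two smaller replies have force. If the Week 8 visit means Week 8a, Induction duration is understated by some days, because dosing continues until Week 8b or mWeek 0; Table 4 of the Phase 2b SAP merges 8a and 8b, so the term is ambiguous. The rounding rule probably means decimal places, which section 5.2.1.6 uses for time since diagnosis. Finally, the Maintenance SAP serves an abbreviated report of a terminated study, so little turns on it there.

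None of this defends the return date itself. The SAPs give no reason for preferring it to a last dose date that they already use.

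**Conclusion.** The point holds as a definitional error in both SAPs. Duration ends at drug return for pre-Week 8 stoppers in Induction and for all subjects over the whole study. This departs from protocol 8.8.1 without being recorded as a change and conflicts with the Phase 2b SAP's own use of the last dose date.

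The size depends on the return visit: up to 0.7 week per subject if it is the discontinuation visit, and 3.6 to 4.7 weeks if it is EOS. The arm-level figures rest on assumed early-stop rates. The consequence is limited to descriptive exposure summaries; the primary and secondary efficacy analyses, the treatment-emergent window and the compliance formula as written are untouched. It is a modest point, worth correcting because the correction is cheap.

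**What to change.** In section 3.7.1 of both SAPs:

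1. Compute duration as (date of last dose taken in the period − date of first dose in the period + 1)/7, with dates from the study drug administration CRF page. Use the return date only when the last dose date is missing.
2. In the Phase 2b SAP, for subjects who continue to Week 8b or mWeek 0, end Induction exposure at the last dose before the first dose of the next period, in line with section 3.1.5.1.
3. Replace 1 significant digit with 1 decimal place, and make the matching change for the standard deviation.

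The cost is SAP wording and a small programming change. The dates are already collected, and no design, sample size or efficacy specification changes.
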